## Abbreviations List

*IVDA: Intravenous Drug Abusers*

*IV: Intravenous*

### Research Summary

**Study Population** N=20 subjects

**Inclusion:**

- The age of the patient is  $\geq 18$ .
- The patient has undergone an urgent or emergent primary cardiac valvar operation as treatment for IVDA endocarditis, with blood cultures positive for *Streptococcus*, *Enterococcus faecalis*, *Staphylococcus aureus*, coagulase-negative *Staphylococci*, or gram-negative organism with susceptibility to an oral antimicrobial with high bioavailability
- The patient has received 2 weeks of postoperative inpatient IV antibiotic therapy with negative blood cultures and no residual active infection by imaging (i.e. computerized axial tomography, echocardiography)
- The patient has the capacity to participate in a compliance tracking tool for medication administration (e.g. a centrally managed core site mobile Medisafe compliance <https://www.medisafe.com/>) as confirmed by both a physician and a care management team member

**Exclusion:**

- Inability to give informed consent
- Residual infection requiring IV antibiotic therapy
- Any persistent secondary noncardiac infection (e.g. infections of solid organs or joints)
- Known poor compliance or deemed incapable to comply with the compliance tracking tool
- Reduced absorption or inability to receive oral treatment due to a gastrointestinal disorder
- Endocarditis attributed to fungal organisms.
- Cancer not otherwise in remission or in need of current or future oncologic therapy
- Medically immunocompromised state
-

- History of habitual noncompliance
- Pregnancy
- Mental incapacity
- Unable to perform local or institutional medical and psychiatric follow up
- Unstable home environment
- Inadequate access to mobile cell service (geographic/rurality)

**Study Design** – Prospective randomized institutional pilot trial of 20 subjects.

Both groups will receive the following support:

1. All patients will enroll in aggressive drug rehabilitation with mandatory participation in a formal psychiatric rehabilitation program for a minimum of 6 weeks (combined inpatient and outpatient),
2. All patients will be followed closely by Infectious Disease specialists
3. All patients will undergo monitoring of treatment efficacy with serum antibiotic levels during the treatment phase
4. All patients will undergo surveillance monitoring of treatment efficacy with blood cultures, and
5. All patients will participate in a compliance tracking tool for medication administration (e.g. a centrally managed core site mobile Medisafe compliance program [<https://www.medisafe.com/>]). All patients and their family/primary care givers receive Medisafe compliance training).

**Patients:** Postoperative patients who have undergone valvar repair or replacement for IVDA endocarditis may be prospectively randomized into two arms:

1. Group I (Experimental Group): 2 weeks of postoperative inpatient IV antibiotic therapy followed by 4 weeks of oral therapy with outpatient follow-up.
2. Group II (Control Group): conventional 2 weeks of postoperative inpatient IV antibiotic therapy followed by 4 weeks of IV antibiotic therapy (inpatient or facility supervised if indwelling catheter utilized).

Subjects will be identified by the study investigators and research coordinators. Once inclusion and exclusion criteria have been met, the patient will be approached by the primary investigator and/or study investigator to present the study. If the patient indicates interest in the study, the study investigator will collaborate with the research coordinator to obtain informed consent.

**Study Duration** – Subjects will be followed for twelve (12) months. Enrollment is expected to take one (1) year to achieve our proposed sample size. Data collection will occur in real-time throughout the study and data analysis will be performed at the conclusion of the study.

## Section II: Design

### Background & Significance

The US opioid epidemic has been implicated in substantial rises in mortality, morbidity, and costs. According to the Centers for Disease Control and Prevention, between 1999 and 2017 there were nearly 218,000 opioid-related deaths in the US, 47,600 in 2017 alone. The staggering rise in recent years is illustrated by a 9.6% increase in the age-adjusted rate of overdose deaths just from 2016 to 2017. States with the highest rates of death due to drug overdose, the majority from intravenous (IV) heroin use, were West Virginia (57.8 per 100,000), Ohio (46.3 per 100,000), Pennsylvania (44.3 per 100,000), the District of Columbia (44.0 per 100,000), and Kentucky (37.2 per 100,000). The increasing rate of drug overdose death has been accompanied by a commensurate increase in the incidence of IV drug-associated (IVDA) acute infective endocarditis.

*The clinical impact of the opioid crisis can be demonstrated by the exponential rise in the incidence and costs associated with IVDA endocarditis. Given the ongoing societal problems with access, addiction, and recidivism, the secondary epidemic of IVDA endocarditis presents a substantial operational, ethical, and financial challenge for health systems and physicians providing essential care for these patients.*

*The current management of acute IVDA endocarditis is associated with unique challenges. Operations are often urgent or emergent due to associated acute secondary hemodynamic embarrassment. Operative complexity is often increased due to multivalve or intracardiac abscess involvement. Postoperative challenges include the need for additional noncardiac procedures, the use of indwelling catheters to deliver prolonged parenteral antibiotics to patients addicted to IV drugs, and the need for ample time for detoxification and addiction counseling to prevent recidivism. Despite the widely held perception that peripherally inserted central catheters are less morbid than traditional central lines, their complication profiles are not dissimilar and life-threatening problems can occur. The management and cost of the appropriate use of indwelling peripheral catheters in IV drug–abusing patients is not trivial. Following successful complex valve operations, patients with incompletely or untreated addiction discharged with these catheters for prolonged IV antibiotics may be often complicated by acute recidivism and early postoperative mortality. For this reason, many institutions have recently adopted a policy of inpatient management until the IV antibiotic course is complete. This prolonged hospitalization period provides time for detoxification, transition from postoperative narcotic pain management to partial opioid antagonists such as buprenorphine for addiction maintenance, and commencement of a crucial component of inpatient drug rehabilitation. This ethically and medically sound policy has an impact on healthcare costs that is unsustainable, however. Moreover, once patients have recovered from a successful operation, the addiction and social issues that led to IV drug abuse may remain. These issues may be significant, because many patients refuse further treatment and sign out of the hospital against medical advice. It is not uncommon for patients to bargain to leave the hospital and even to request permission to take oral antibiotics and attempt to enroll in an inpatient drug rehabilitation program closer to home.*

*Early transition to oral antibiotic therapy in the postoperative management of endocarditis may provide several advantages. Should this be found to be safely applicable to postoperative IVDA endocarditis patients, these benefits may be further compounded. Advantages include a reduction in catheter-related complications, decreased LOS, an earlier return to normal function, and reduced cost. Should an increase in compliance be facilitated with simpler oral administration, this would facilitate earlier intensive addiction counseling and drug rehabilitation. Of course, such an option might not be appropriate for all patients with IVDA endocarditis, such as those in whom secondary noncardiac infection may persist (solid organs or joints), or for those with endocarditis attributed to fungal organisms.*

## **Objectives**

**Purpose** – *The purpose of this post-operative institutional pilot trial is to ascertain the safety and compliance of initial IV antibiotic followed by oral therapy following uncomplicated IVDA endocarditis. Endocarditis has a high rate of morbidity and mortality, involves prolonged hospitalization and prolonged use of IV antibiotics necessitating six (6) weeks of in-patient stay, and comes with a high cost.*

**Primary Objective** – *To assess all-cause mortality, recurrent blood culture positive infection, or cardiac re-operation at six (6) months and twelve (12) months.*

**Secondary Objective(s)** – *To assess all-cause mortality, readmission for recurrent infection or cardiac re-operation, and cost at six (6) and twelve (12) months.*

**Rationale:** *The key principle of this hybrid pathway (regional or smaller scale trial) is to focus on both “implementation science” and “effectiveness”:*

- **Effectiveness:** *This study will document that in postoperative patients who have undergone valve repair or replacement as treatment for IV drug–associated (IVDA) endocarditis:*

- Will ascertain safety and compliance for 2 weeks of postoperative IV antibiotics followed by 4 weeks of oral antibiotics versus 6 weeks of conventional postoperative IV antibiotics
- **Implementation science:** This study will document that patients managed with either arm of the protocol can achieve compliance with and graduation from a drug rehabilitation program. The implementation science portion of this trial will place particular emphasis on the measurement of compliance (e.g. a centrally managed core site mobile Medisafe compliance program [<https://www.medisafe.com/>]).

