### **Study Population** N=20 subjects

#### **Inclusion:**

- The age of the patient is  $\geq 18$ .
- The patient has undergone an urgent or emergent primary cardiac valvar operation as treatment for IVDA endocarditis, with blood cultures positive for *Streptococcus*, *Enterococcus faecalis*, *Staphylococcus aureus*, coagulase-negative *Staphylococci*, or gram-negative organism with susceptibility to an oral antimicrobial with high bioavailability.
- The patient has received 2 weeks of postoperative inpatient IV antibiotic therapy with negative blood cultures and no residual active infection by imaging (i.e. computerized axial tomography, echocardiography)
- The patient has the capacity to participate in a compliance tracking tool for medication administration (e.g. a centrally managed core site mobile Medisafe compliance <https://www.medisafe.com/>) as confirmed by both a physician and a care management team member

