#### **Exclusion:**

- Inability to give informed consent
- Residual infection requiring IV antibiotic therapy
- Any persistent secondary noncardiac infection (e.g. infections of solid organs or joints)
- Known poor compliance or deemed incapable to comply with the compliance tracking tool
- Reduced absorption or inability to receive oral treatment due to a gastrointestinal disorder
- Endocarditis attributed to fungal organisms.
- Cancer not otherwise in remission or in need of current or future oncologic therapy
- Medically immunocompromised state
- History of habitual noncompliance
- Pregnancy
- Mental incapacity
- Unable to perform local or institutional medical and psychiatric follow up
- Unstable home environment
- Inadequate access to mobile cell service (geographic/rurality)

**Study Design** – Prospective randomized institutional pilot trial of 20 subjects.

Both groups will receive the following support:

1. All patients will enroll in aggressive drug rehabilitation with mandatory participation in a formal psychiatric rehabilitation program for a minimum of 6 weeks (combined inpatient and outpatient),
2. All patients will be followed closely by specialists in Infectious Disease
3. All patients will undergo monitoring of treatment efficacy with serum antibiotic levels during the treatment phase
4. All patients will undergo surveillance monitoring of treatment efficacy with blood cultures, and
5. All patients will participate in a compliance tracking tool for medication administration (e.g. a centrally managed core site mobile Medisafe compliance program [<https://www.medisafe.com/>]. All patients and their family/primary care givers receive Medisafe compliance training).

**Patients:** Postoperative patients who have undergone valvar repair or replacement for IVDA endocarditis may be prospectively randomized into two arms:

1. Group I (Experimental Group): 2 weeks of postoperative inpatient IV antibiotic therapy followed by 4 weeks of oral therapy with outpatient follow-up.
2. Group II (Control Group): conventional 2 weeks of postoperative inpatient IV antibiotic therapy followed by 4 weeks of IV antibiotic therapy (inpatient or facility supervised if indwelling catheter utilized).

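### The secondary readmission component gives the arms unequal opportunity to record an event in the first 4 weeks after randomisation, which counts against the oral arm to the extent that controls remain in hospital

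*Combined protocol and SAP*

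**What the plan says.** The Objectives section gives the secondary objective as "To assess all-cause mortality, readmission for recurrent infection or cardiac re-operation, and cost at six (6) and twelve (12) months". The primary objective just above it is "To assess all-cause mortality, recurrent blood culture positive infection, or cardiac re-operation at six (6) months and twelve (12) months", which carries no readmission condition.

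The treatment setting differs by arm (Study Design, under Patients). Group I receives "2 weeks of postoperative inpatient IV antibiotic therapy followed by 4 weeks of oral therapy with outpatient follow-up". Group II has the same two inpatient weeks, "followed by 4 weeks of IV antibiotic therapy (inpatient or facility supervised if indwelling catheter utilized".

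The time of randomisation is not stated. It is implied by an inclusion criterion: "The patient has received 2 weeks of postoperative inpatient IV antibiotic therapy with negative blood cultures". Patients are approached only once the criteria are met.

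Nothing in the protocol or its Statistical Analysis Plan section defines readmission, says how a recurrence during a continuing hospital stay is counted, says whether a transfer from facility to hospital is a readmission, or fixes the start of the 6- and 12-month windows. The analysis paragraph lists generic methods only.

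**The concern.** Only a discharged patient can be readmitted. Take two patients with the same recurrence three weeks after randomisation. The oral-arm patient comes back to hospital and is counted. A control who is still an inpatient is treated within the continuing stay and, on the wording as it stands, is not counted. The endpoint then records where the patient was as well as whether the infection returned.

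The counting may also vary within the control arm, because a facility patient sent to hospital might or might not be classed as readmitted.

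The trial is meant to assess the safety of the oral strategy, and the protocol expects later studies to build on it. A spurious excess of recurrence on oral therapy, even in a secondary component, would point those studies the wrong way. The primary endpoint covers part of the gap, since it counts death, re-operation and culture-positive recurrence wherever they occur. A recurrence diagnosed without a positive blood culture could enter only through the secondary component.

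**Working it through.** The plan has no figure of its own to reproduce here. Its only design number is 20 patients, with no event rate, effect size or power. The check therefore sizes the artefact when true risk is equal in both arms.

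**Inputs from the protocol**
- Period in which the settings differ: 4 weeks (Group I and Group II descriptions).
- Windows: 6 and 12 months, taken as W = 26 and 52 weeks from randomisation.

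**Assumptions (not in the documents)**
- True risk p of a qualifying event over the window: 10–40%, the same in both arms.
- Share f of controls who are inpatients for all 4 weeks: 0, 0.5 or 1.
- Oral-arm patients are discharged at randomisation.
- 10 patients per arm; the allocation ratio is not stated.

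**Step 1: window lost.** For a control inpatient, 4/26 = 15.4% of the 6-month window and 4/52 = 7.7% of the 12-month window.

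**Step 2: constant hazard.** Risk counted in control = f × [1 − (1 − p)^((W − 4)/W)] + (1 − f) × p. Risk counted in the oral arm = p.

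Example with p = 0.20 and f = 1:
- 6 months: 1 − 0.8^(22/26) = 0.172, a gap of 2.8 points.
- 12 months: 1 − 0.8^(48/52) = 0.186, a gap of 1.4 points.

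| True risk (= oral arm) | Control, 6 mo, f = 1 | Gap (points) | Gap, f = 0.5 | Control, 12 mo, f = 1 | Gap (points) |
|---|---|---|---|---|---|
| 10% | 8.5% | 1.5 | 0.7 | 9.3% | 0.7 |
| 20% | 17.2% | 2.8 | 1.4 | 18.6% | 1.4 |
| 30% | 26.1% | 3.9 | 2.0 | 28.1% | 2.0 |
| 40% | 35.1% | 4.9 | 2.5 | 37.6% | 2.4 |

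Gaps are rounded from unrounded values. With f = 0 every gap is zero.

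**Step 3: early events.** If a share e of events falls in the first 4 weeks and f = 1, the gap is p × e. With p = 20%, e = 25% gives 5 points and e = 50% gives 10 points (20% against 10%). With p = 40%, the same shares give 10 and 20 points.

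**Step 4: patients.** With 10 per arm, the constant-hazard gap at 6 months is about 0.1 to 0.5 of an event. The early-event scenarios, for true risks of 20–40%, give 0.5 to 2 events.

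**Step 5: after the change.** If events count in any setting, the definition contributes no difference between the arms.

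**The case against.** A reader might infer that controls cannot be readmitted at all before week 6, so that the component is biased by construction. The documents do not support that. Group II therapy may be facility supervised, and such patients can be admitted to hospital. The Background also says that "many patients refuse further treatment and sign out of the hospital against medical advice", and controls who leave early can be readmitted too. The bias depends on the share who remain inpatients, which is not given. It is unlikely to be nil, since the Objectives describe "prolonged use of IV antibiotics necessitating six (6) weeks of in-patient stay" as the current pattern of care.

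A reader might also take a doubling (20% against 10%) as the expected size. That figure needs half of all events to fall within 4 weeks of randomisation and every control to be an inpatient. Neither has a source in the documents, so it is a scenario and not an estimate.

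Four further points carry weight:
- The sentence can be parsed as readmission for infection, or re-operation in any setting. Re-operation is then unaffected, but the infection part still is.
- The primary endpoint, and the mortality and cost parts of the secondary objective, do not require a readmission. Surveillance blood cultures in all patients give culture-positive recurrence a route to capture in both arms. Recurrence without a positive culture has no such route.
- Randomisation at week 2 is inferred, and immediate discharge is not established. Both arms must complete at least 6 weeks of rehabilitation that combines inpatient and outpatient care. A later discharge on oral therapy would shrink the gap.
- Readmission is listed beside cost and is a legitimate resource-use outcome of earlier discharge. That is a reason to keep it as such, not to let it stand for recurrence.

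**Conclusion.** The concern holds in a limited form. Opportunity for readmission differs by arm over about 4 weeks, and no counting rule corrects for this. For each control who stays in hospital, the direction is against the oral arm.

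Under equal true risk of 10–40%, constant hazard and all controls inpatient, the artefact is about 1.5–4.9 points at 6 months and 0.7–2.4 at 12 months. With half of controls inpatient it is 0.7–2.5 points at 6 months. It grows if events come early and vanishes if no control remains in hospital. The event risks, the inpatient share, the event timing, discharge at randomisation and equal allocation are all assumptions.

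Severity is below must-fix. This is one component of a secondary objective, and the primary endpoint is unaffected by admission status.

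**What to change.** In Objectives, replace the readmission component with:

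> *Recurrent infection or cardiac re-operation at any time from randomisation, in any setting (index stay, facility, outpatient or readmission).*

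State that recurrent infection here includes cases without a positive blood culture, and by what criteria they are diagnosed. State the time of randomisation and start both windows there.

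Report readmission separately as resource use, with a definition that says how a facility-to-hospital transfer is counted. It could stand alongside days alive and out of hospital from randomisation. That measure will reflect the planned difference in stay, so it should not be read as evidence on recurrence. Count readmission from discharge rather than only from week 6, because a week-6 start would drop the oral arm's first weeks at home.

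The cost is a few sentences and somewhat more event ascertainment, including obtaining records from outside facilities.

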## Study Design & Methodology

*This is a prospective pilot post-operative institutional study to ascertain safety and compliance of initial IV antibiotic followed by oral therapy following uncomplicated IVDA endocarditis. Data will be collected to ascertain safety and compliance of initial IV antibiotic followed by oral therapy following uncomplicated IVDA endocarditis.*

*There may be no direct benefit to study participants, but this research will make a significant contribution to the scientific field and general population. Future studies that can further inform the care of these subjects can be built upon the results from this study.*

## Target Population & Recruitment Methods

*Prospective randomized institutional pilot trial of 20 subjects. This is a pilot post-operative institutional trial to ascertain safety and compliance therefore sample size is adequate.*

### **Study Population** N=20 subjects

#### **Inclusion:**

- The age of the patient is  $\geq 18$ .
- The patient has undergone an urgent or emergent primary cardiac valvar operation as treatment for IVDA endocarditis, with blood cultures positive for *Streptococcus*, *Enterococcus faecalis*, *Staphylococcus aureus*, coagulase-negative *Staphylococci*, or gram-negative organism with susceptibility to an oral antimicrobial with high bioavailability.
- The patient has received 2 weeks of postoperative inpatient IV antibiotic therapy with negative blood cultures and no residual active infection by imaging (i.e. computerized axial tomography, echocardiography)
- The patient has the capacity to participate in a compliance tracking tool for medication administration (e.g. a centrally managed core site mobile Medisafe compliance <https://www.medisafe.com/>) as confirmed by both a physician and a care management team member

#### **Exclusion:**

- Inability to give informed consent
- Residual infection requiring IV antibiotic therapy
- Any persistent secondary noncardiac infection (e.g. infections of solid organs or joints)
- Known poor compliance or deemed incapable to comply with the compliance tracking tool
- Reduced absorption or inability to receive oral treatment due to a gastrointestinal disorder
- Endocarditis attributed to fungal organisms.
- Cancer not otherwise in remission or in need of current or future oncologic therapy
- Medically immunocompromised state
- History of habitual noncompliance
- Pregnancy
- Mental incapacity
- Unable to perform local or institutional medical and psychiatric follow up
- Unstable home environment
- Inadequate access to mobile cell service (geographic/rurality)

**Study Design** – Prospective randomized institutional pilot trial of 20 subjects.

Both groups will receive the following support:

1. All patients will enroll in aggressive drug rehabilitation with mandatory participation in a formal psychiatric rehabilitation program for a minimum of 6 weeks (combined inpatient and outpatient),
2. All patients will be followed closely by specialists in Infectious Disease
3. All patients will undergo monitoring of treatment efficacy with serum antibiotic levels during the treatment phase
4. All patients will undergo surveillance monitoring of treatment efficacy with blood cultures, and
5. All patients will participate in a compliance tracking tool for medication administration (e.g. a centrally managed core site mobile Medisafe compliance program [<https://www.medisafe.com/>]. All patients and their family/primary care givers receive Medisafe compliance training).

**Patients:** Postoperative patients who have undergone valvar repair or replacement for IVDA endocarditis may be prospectively randomized into two arms:

1. Group I (Experimental Group): 2 weeks of postoperative inpatient IV antibiotic therapy followed by 4 weeks of oral therapy with outpatient follow-up.
2. Group II (Control Group): conventional 2 weeks of postoperative inpatient IV antibiotic therapy followed by 4 weeks of IV antibiotic therapy (inpatient or facility supervised if indwelling catheter utilized).

Subjects will be identified by the study investigators and research coordinators. Once Inclusion and Exclusion criteria have been met, the patient will be approached by the primary surgeon and/or study investigator to present the study. If the patient indicates interest in the study, the study investigator will collaborate with the research coordinator to obtain informed consent.

**Study Duration** – Subjects will be followed for twelve (12) months. Enrollment is expected to take one (1) year to achieve our proposed sample size. Data collection will occur real-time throughout the study and data analysis will be performed at the conclusion of the study.

